Determine if extended-release triamcinolone acetonide treatment alters the progression of cartilage degradation following ACL reconstruction. The change in a urinary biomarker of cartilage degradation (CTXII) between baseline and the 4-month postoperative follow-ups be compared between the treatment and placebo groups. Following cartilage degradation, CTXII (C-terminal crosslinked telopeptide type II collagen) is released into the synovial fluid, is circulated and then filtered by the kidneys. CTXII has been identified as a biomarker for the diagnosis, staging, and evaluating the prognosis of hip and knee OA, and has also been demonstrated to be responsive over short testing periods (3 months). We have reported that CTXII correlates with the degree of joint destruction and increases significantly within 1 month after ACL injury. CTXII will be measured in the urine by ELISA (Cartilaps® (CTX-II); Immunodiagnostic Systems, Inc, Fountain Hills, AZ) and will be normalized to creatinine levels (Quidel, San Diego, CA).

Biological data quality control: To ensure data quality and fidelity, all data collection and analysis procedures will be detailed in a structured manual. OA biomarker data collected will be carefully analyzed with respect to variability, linear range of standard, and need for repeat analyses. Controls provided with commercially available ELISA kits will be used with every run. For assays for which no control is available or provided, aliquots of serum from normal human subjects have been aliquoted and frozen at -80oC for this purpose. Each assay day, a fresh aliquot of this control serum is thawed and used on every plate to calculate intra- and inter-assay variance of the assay. In addition to the standard curve run in duplicate, this control will be run with each assay and the results used to determine the precision of the assay and to establish an acceptable control range for the assay. The mean of the control sample for all assays ± 2 standard deviations is defined as the acceptable control range. Any samples on a plate in which the control falls outside of this range will be excluded and repeated. Samples will be run in duplicate and reanalyzed if the coefficient of variation is $> 15\%$. For values that are below the level of detection, a value equivalent to 0.5 lowest limit of detection will be recorded and used for statistical analyses. Our team in Kentucky has used this methodology in prior works.

COVARIATES

Biomarker concentrations have been previously shown to differ based on patient age, sex, race, and BMI.⁵⁰ As such, these patient factors will be collected and used as covariates in our statistical analyses.

SAFETY AND OTHER ASSESSMENTS

- Limited Physical examination: Subject height and weight will be monitored, and the injection site will be closely monitored for infection and/or allergic reaction.
- Vital signs: Blood pressure will be assessed per the standard of care
- Radiographic or other imaging assessments: The amount of arthritic changes to the knee will be assessed by the Principal Investigator from each patient's routine standard of care preoperative x-ray. Patients with more than Kellgren Lawrence grade I changes will be excluded from the study. These images will not be reviewed until after the patient has signed a HIPAA-approved informed consent form.
- Assessment of adverse events: Patients that develop AEs/SAEs will be closely monitored until conclusion of the event. For events that are ongoing at the 6-week study visit, we will continue to contact the patient on a monthly basis until the event has resolved or deemed to have reached maximum medical improvement.

All information garnered from safety assessments will be recorded in the patient's medical chart.

Attachments

Data Collection & Research Materials

In this section, please provide the following:

- Describe all sources or methods for obtaining research materials about or from living individuals (such as specimens, records, surveys, interviews, participant observation, etc.), and explain why this information is needed to conduct the study.
- For each source or method described, please list or attach all data to be collected (such as genetic information, interview scripts, survey tools, data collection forms for existing data, etc.).
- If you will conduct a record or chart review, list the beginning and end dates of the records you will view.

Data collection is the responsibility of the clinical trial staff at the site under the supervision of the site investigator. The investigator is responsible for ensuring the accuracy, completeness, legibility, and timeliness of the data reported.

All source documents should be completed in a neat, legible manner to ensure accurate interpretation of data.

Hardcopies of the study visit worksheets will be provided for use as source document worksheets for recording data for each participant enrolled in the study. Clinical data will be entered onto paper case report forms provided by the sponsor. Clinical data will be transcribed directly from the source documents.

The investigator must give the monitor access to relevant hospital or clinical records to confirm their consistency with the paper CRF entries. Monitoring standards require full verification for the presence of informed consent, adherence to the exclusion criteria, documentation of SAEs, and the recording of primary efficacy and safety variables. Additional checks of the consistency of the source data with the CRFs are to be performed according to the study-specific monitoring plan.

Attachments

Resources

Describe the availability of the resources and adequacy of the facilities that you will use to perform the research. Such resources may include:

- Staffing and personnel, in terms of availability, number, expertise, and experience;
- Computer or other technological resources, mobile or otherwise, required or created during the conduct of the research;
- Psychological, social, or medical services, including equipment needed to protect subjects, medical monitoring, ancillary care, or counseling or social support services that may be required because of research participation;
- Resources for communication with subjects, such as language translation/interpretation services.

Data collection will take place at the University of Kentucky's Orthopaedic and Sports Medicine Center and the Sports Medicine Research Institute. The participants will be followed by the principal investigator and their research team which includes physicians, certified nurses, and clinical research coordinators during the study. Emergency medical equipment, medications and supplies will be at the physician's disposal should the participant have an acute untoward reaction.

Potential Risks & Benefits

Risks

- Describe any potential risks – including physical, psychological, social, legal, ability to re-identify subjects, or other risks. Assess the seriousness and likelihood of each risk.
- Which risks may affect a subject's willingness to participate in the study?
- Describe likely adverse effects of drugs, biologics, devices or procedures participants may encounter while in the study.

- *Qualitative research* - describe ethical issues that could arise while conducting research in the field and strategies to handle those situations.
- Describe any steps to mitigate these risks.

Benefits

- Describe potential direct benefits to study participants – including diagnostic or therapeutic, physical, psychological or emotional, learning benefits. This cannot include incentives or payments.
- State if there are no direct benefits.
- Describe potential benefits to society and/or general knowledge to be gained.

Describe why potential benefits are reasonable in relation to potential risks. If applicable, justify why risks to vulnerable subjects are reasonable to potential benefits.

Knee Aspiration: As with any invasive procedure, complications can occur. Some possible complications may include, but are not limited to, the following:

- Fever
- Pain or discomfort at the aspiration site
- Bruising at the aspiration site
- Redness, swelling, bleeding or other drainage from the aspiration site
- Infection at the aspiration site

MRI: The risks from MRI are minimal. The images taken will be taken of the knee cartilage. They are used only for research and are not read for any clinical interpretation.

Possible Risk/Side Effect from MR Scanning include Claustrophobia (It occasionally occurs, can be treated, and the volunteer is removed from the magnet) and Loud noise (It is expected to occur, is not serious, and participants wear ear protection).

KNOWN POTENTIAL RISKS OF ZILRETTA

Previous studies of animal models have suggested that repeated, high doses of intra-articular corticosteroid injection can adversely affect articular cartilage. In human studies of older patients with knee OA, repeated triamcinolone acetonide injections may result in cartilage thinning or loss of cartilage volume; however, little confirmatory evidence is available in human trials or when used intra-articularly at either lower doses or frequency following acute injury.

The following risks are copied directly from the Zilretta package insert:

CONTRAINDICATIONS: Patients with hypersensitivity to triamcinolone acetonide or any component of the product.

WARNINGS AND PRECAUTIONS

Warnings and Precautions Specific for ZILRETTA

ZILRETTA has not been evaluated and should not be administered by the following routes:

- Epidural
- Intrathecal
- Intravenous
- Intraocular
- Intramuscular
- Intra-dermal
- Subcutaneous

1. **Serious Neurologic Adverse Reactions with Epidural and Intrathecal Administration:** Serious neurologic events, some resulting in death, have been reported with epidural injection of corticosteroids. Specific events reported include, but are not limited to, spinal cord infarction, paraplegia, quadriplegia, cortical blindness, and stroke. These serious neurologic events have been reported with and without use of fluoroscopy. Reports of serious medical events have been associated with the intrathecal route of corticosteroid administration. The safety and effectiveness of epidural and intrathecal administration of corticosteroids have not been established, and corticosteroids are not approved for this use. In particular, the formulation of ZILRETTA should not be considered safe to use for epidural or intrathecal administration.

2. **Hypersensitivity Reactions:** Rare instances of anaphylaxis have occurred in patients with hypersensitivity to corticosteroids. Cases of serious anaphylaxis, including death, have been reported in individuals receiving triamcinolone acetonide injection, regardless of the route of administration. Institute appropriate care upon occurrence of an anaphylactic reaction.

3. **Joint Infection and Damage:** Intra-articular injection of corticosteroid may be complicated by joint infection. A marked increase in pain accompanied by local swelling, further restriction of joint motion, fever, and malaise are suggestive of septic arthritis. If this complication occurs and a diagnosis of septic arthritis is confirmed, institute appropriate antimicrobial therapy. Avoid injection of a corticosteroid into an infected site. Local injection of a corticosteroid into a previously infected joint is not usually recommended. Examine any joint fluid present to exclude a septic process. Corticosteroid injection into unstable joints is generally not recommended. Intra-articular injection may result in damage to joint tissues.

4. **Increased Risk of Infections:** Intra-articularly injected corticosteroids are systemically absorbed. Patients who are on corticosteroids are more susceptible to infections than are healthy individuals. There may be decreased resistance and inability to

localize infection when corticosteroids are used. Infection with any pathogen (viral, bacterial, fungal, protozoan, or location of the body may be associated with the use of corticosteroids alone or in combination with other immunosuppressive agents. These infections may be mild to severe. With increasing doses of corticosteroids, the rate of occurrence of infectious complications increases. Corticosteroids may also mask some signs of current infection. Advise patients to inform their health care provider if they develop fever or other signs or symptoms of infection. Advise patients who have not been vaccinated to avoid exposure to chicken pox or measles. Instruct patients to contact their health care provider immediately if they are exposed.

5. Alterations in Endocrine Function: Corticosteroids can produce reversible hypothalamic-pituitary-adrenal axis suppression, with the potential for adrenal insufficiency after withdrawal of treatment, which may persist for months. In situations of stress during that period (as in trauma, surgery, or illness), institute corticosteroid replacement therapy. Metabolic clearance of corticosteroids is decreased in hypothyroid patients and increased in hyperthyroid patients.

6. Cardiovascular Effects: Corticosteroids can cause elevations of blood pressure, salt and water retention, and increased excretion of potassium. These effects are less likely to occur with synthetic derivatives. Monitor patients with congestive heart failure or hypertension for signs of edema, weight gain, and imbalance in serum electrolytes. Dietary salt restriction and potassium supplementation may be necessary.

7. Renal Effects: Corticosteroids can cause salt and water retention, and increased excretion of potassium. These effects are less likely to occur with synthetic derivatives. All corticosteroids increase calcium excretion. Monitor patients with renal insufficiency for signs of edema, weight gain, and imbalance in serum electrolytes. Dietary salt restriction and potassium supplementation may be necessary.

8. Increased Intraocular Pressure: Corticosteroid use may be associated with development or exacerbation of increased intraocular pressure. Monitor patients with elevated intraocular pressure for potential treatment adjustment.

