- [FDA Diversity Guidance](#)

This study will recruit a sample of 30 skeletally mature male and female participants between the ages of 18 and 40 that have undergone arthroscopic ACL reconstruction with partial meniscectomy or meniscal repair. Participants will be recruited from the University of Kentucky's Department of Orthopaedic Surgery & Sports Medicine clinical patient population.

Complete subject inclusion and exclusion criteria are as follows, and patients will not be excluded on the basis of sex, race, or ethnicity:

Inclusion Criteria:

1. Written consent to participate in the study
2. Male or female greater than or equal to 18 years of age and less than 99 years of age
3. Has undergone arthroscopic ACL reconstruction with partial meniscectomy or meniscal repair in the past 4 weeks
4. Ambulatory and in good general health
5. Willing and able to comply with the study procedures and visit schedules and able to follow verbal and written instructions.
6. Willing to abstain from use of protocol-restricted medications during the study
7. Females and males who have reproductive potential: Must use highly effective contraception for at least 1 month prior to the study injection and agreement to use such a method during study participation (18 weeks; 8 to 26 weeks after surgery)
8. Demonstrate persistent inflammation defined as either synovial fluid IL-1alpha concentration >= 5 pg/mL at the time of surgery

Exclusion Criteria:

1. Known allergic reactions to components of the extended-release triamcinolone acetonide (Zilretta®)
2. Reactive arthritis, rheumatoid arthritis, psoriatic arthritis, ankylosing spondylitis, or arthritis associated with inflammatory bowel disease
3. History of infection in either knee joint
4. Clinical signs and symptoms of active knee infection or crystal disease in either knee within 1 month of Screening
5. Other surgery or arthroscopy of either knee within 6 months of Screening
6. Intraarticular treatment of any joint with any of the following agents within six (6) months of Screening: any corticosteroid preparation or any biologic agent (e.g., platelet rich plasma (PRP) injection, stem cells, prolotherapy, amniotic fluid injection; investigational or marketed).
7. Intraarticular treatment in either knee with hyaluronic acid (investigational or marketed) within 6 months of Screening
8. Parenteral or oral corticosteroids (investigational or marketed) within 3 months of Screening

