- Use one of the attachment buttons in this section, or under the Additional Information section to include the information with your application. During the document upload process, you will be able to provide a brief description of the attachment.

Background

Include a brief review of existing literature in the area of your research. You should identify gaps in knowledge that should be addressed and explain how your research will address those gaps or contribute to existing knowledge in this area. For interventional research, search PubMed and ClinicalTrials.gov for duplicative ongoing and completed trials with same condition and intervention(s).

We have shown that anterior cruciate ligament (ACL) injury initiates a biochemical cascade that leads to cartilage degradation and the development of posttraumatic osteoarthritis (PTOA).⁵⁻⁸ ACL and acute traumatic meniscus tears have been linked the development and progression of PTOA.⁹⁻¹² As such, there is an unmet need to identify treatments that may alter the progression of PTOA following ACL meniscus injury. Our overarching hypothesis is that intraarticular administration of long-acting anti-inflammatory agents will alter the progression of PTOA following ACL reconstruction.

The current standard of care for patients with combined ACL and meniscus injuries consists of surgical treatment often with a short course of postoperative physical therapy. However, the current mechanically-based standard of care does not address the persistent inflammatory process that promotes cartilage degradation and PTOA progression. We have demonstrated that pro-inflammatory stimulation of meniscus cells increases matrix metalloproteinase (MMP) and cytokine activity,¹³ and the combination of pro-inflammatory cytokines and compressive loading like what may be seen during sporting and high demand activities further results in degradative enzyme activity and increased production of pro-inflammatory mediators.¹⁴ In this way, the meniscus plays an active role in promoting the cycle of articular cartilage degradation and PTOA progression after ACL reconstruction.

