Patient will provide informed consent prior to undergoing ACL reconstruction with meniscal involvement. At the time of surgery, a knee aspiration will be performed in the operating room after the patient has been anesthetized so that synovial fluid can be collected. Synovial fluid samples will be assessed for the concentration of pro-inflammatory cytokine IL-1alpha. This will be done to identify patients that present with persistent inflammation after injury that may be at increased risk of cartilage degradation. Patients with elevated IL-1alpha, defined as synovial fluid concentrations ≥ 5 pg/mL, will then be randomized to one of two groups. The synovial fluid threshold of 5 pg/mL was based on our previously published study of ACL patients that demonstrated that those with elevated IL-1alpha at the time of surgery less likely to achieve a successful clinical outcome at 2 years (Latttermann et al., Biomed Res Int, 2018).

Eight weeks after surgery, the knee will be aspirated and one group will receive a single 32 mg Zilretta injection and the other group will receive a 5 mL saline injection. The syringes will be blinded to ensure that both the investigator administering the injection and the patient will be blinded to the group assignment. Patients will then be seen again six weeks later. Both prior to injection and at the 6-month follow-up visit, patients will undergo 3T MRI scans so that femoral shape can be assessed and will also be asked to complete patient-reported outcomes questionnaires and provide a urine sample.

Attachments

Subject Recruitment Methods & Advertising

Describe how the study team will identify and recruit subjects. Please consider the following items and provide additional information as needed so that the IRB can follow each step of the recruitment process.

- How will the study team identify potential participants?
- Who will first contact the potential subjects, and how?
- Will you use advertisements? If so, how will you distribute those?
- How and where will the research team meet with potential participants?
- If applicable, describe proposed outreach programs for recruiting women, minorities, or disparate populations.
- How you will minimize undue influence in recruitment?
- Attach copies of all recruiting and advertising materials (emails, verbal scripts, flyers, posts, messages, etc.).

For additional information on recruiting and advertising:

- [IRB Application Instructions - Advertisements](#)

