- [PI Guide to Identification and Recruitment of Human Subjects for Research](#)

This single site study will include 30 patients that have undergone ACL reconstruction with partial meniscectomy or meniscal repair. Our group performs 224 primary ACL reconstructions per year, with 154 (69%) patients/year meeting the inclusion criteria for this study. Based on our current and recent randomized trials assessing interventions prior to or following ACL reconstruction (ClinicalTrials.gov Identifiers: NCT02930122, NCT03364647, NCT03429140) we anticipate a similar rate of eligible patients that agree to participate in the current study (76%). Extrapolating from our annual patient volume, RCT agreement rate, and an approximate 30% rate of patients with persistent inflammation, we do not anticipate difficulty in enrolling 100 patients over an 18 month period in order to yield our desired sample size of 30 patients. Furthermore, our established relationship with other clinicians, dedicated research personnel with dedicated research space in our clinical facility also support the feasibility of successfully completing the proposed project.

- Accrual Rate: Enroll 10 patients per month with 3 patients per month with qualifying levels of IL-1alpha
- Patients will be recruited from the outpatient clinical populations of the UK HealthCare sports medicine surgeons at the UK HealthCare Orthopaedic and Sports Medicine Center
- Potentially eligible patients will be identified by their surgeon during a regularly scheduled preoperative visit. Patients will then meet with a member of the research team to discuss the study, determine eligibility, and provide informed consent.
- No advertisement will be used for this study.
- Since study visits coincide with routine standard of care follow-up visits 8 weeks and 6 months after surgery, patients will be reminded of their visit by the UKHealthCare automated phone reminder system. In addition, research personnel will contact patients via the patient's preferred method of contact (phone, text message, and/or email) 2 days prior to their visit to remind the patient of their upcoming visit.

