Determine if extended-release triamcinolone acetonide treatment alters progressive changes in bone shape after ACL reconstruction. The bone area of the medial femoral condyl has been shown to increase within the first few months after ACL reconstruction. This is clinically meaningful as similiary bony changes have been previously associated with progressive OA and within 6 months of ACL reconstruction correlated with subsequent patient-reported outcomes and MRI markers of cartilage quality at 3 years. All subjects will undergo MRI examination prior to undergoing the study injection at Visit 3 and again at Visit 4. Sagittal and axial MRI images will be acquired with the knee in full extension using a 3.0-T MRI scanner and an 1Tx/15Rx phased array knee coil. Sagittal and axial T1-weighted spin echo images (FSE) will be acquired to allow semi-quantitative analysis at the conclusion of the study. These sequences will be followed by a sagittal high-resolution 3D dual echo steady state (DESS) sequence for cartilage segmentation and a sagittal combined T1/T2 mapping for the quantification of cartilage composition.

Bone volume of the medial femoral condyle will be measured using previously validated methods. A single investigator experienced with quantitative and semi-quantitative assessments of knee MRIs⁴¹, will manually segment the medial femoral condyle on each slice of the MRI. Since the thickness of each slice is 3.5 mm, we will then calculate the medial condyle volume on each slice and then sum the volumes of all slices to generate the total medial condyle volume.

SECONDARY OBJECTIVES

Compare the change in patient-reported outcomes between patients treated with extended release triamcinolone acetonide or placebo following ACL reconstruction. The change in patient-reported outcomes (IKDC score, KOOSglobal score, and the Intermittent and Constant Osteoarthritis Pain (ICOAP) score) between the date of injection and the 6-month, 1-year, and 2-year postoperative follow-ups. The IKDC and KOOSglobal are knee-related patient-reported outcome tools. The IKDC has been validated in this specific patient population, and we developed and validated the KOOSglobal for use with young and potentially more active patient populations. The ICOAP was developed as part of the OARSI/OMERACT initiative and is a valid and reliable tool to assess OA-related pain.

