Does your research fall under the purview of any of the other review committees listed below? *[If yes, check all that apply and attach applicable materials using the attachment button at the bottom of your screen.]*

Yes No

Additional Information

- Institutional Biosafety Committee
- Radiation Safety Committee
- Radioactive Drug Research Committee
- Markey Cancer Center (MCC) Protocol Review and Monitoring Committee (PRMC)
- Graduate Medical Education Committee (GME)
- Office of Medical Education (OME)

- [Institutional Biosafety Committee \(IBC\)](#) - Attach required IBC materials
- [Radiation Safety Committee \(RSC\)](#) - For applicability, see instructions and attach form
- [Radioactive Drug Research Committee \(RDRC\)](#)
- [Markey Cancer Center \(MCC\) Protocol Review and Monitoring Committee \(PRMC\)**](#) - Attach MCC PRMC materials, if any, per instructions.
- [Office of Medical Education \(OME\)](#)
- [Graduate Medical Education Committee \(GME\)](#)

Attachments

**** If your study involves cancer research, be sure to select "Cancer Research" in the "Research Attributes" section.** ORI will send your research protocol to the Markey Cancer Center (MCC) Protocol Review and Monitoring Committee (PRMC). The [MCC PRMC](#) is responsible for determining whether the study meets the National Cancer Institute (NCI) definition of a clinical trial and for issuing documentation to you (the investigator) which confirms either that PRMC approval has been obtained or that PRMC review is not required. Your IRB application will be processed and reviewed independently from the PRMC review.

53136 Statistical Analysis Plan:

Primary objective will be assessed using two-tailed independent t-tests for comparison between timepoints. Similarly, all secondary measures will be assessed using two-tailed independent t-tests.

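### Partial meniscectomy and meniscal repair are both eligible, but no stratification by procedure is stated and the planned t-tests do not adjust for it

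*Combined protocol and SAP*

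**What the plan says.** Study Population describes 30 participants who "have undergone arthroscopic ACL reconstruction with partial meniscectomy or meniscal repair", and the inclusion criteria repeat the same two operations. Neither place gives a quota or an expected split.

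On allocation, Study Design says that patients with elevated IL-1alpha "will then be randomized to one of two groups", and Background is equally brief. No ratio, sequence method, blocking or stratification factor is stated anywhere.

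The primary measure is on the medial side of the knee (Research Procedures, Primary Objective): "Bone volume of the medial femoral condyle will be measured using previously validated methods". It is taken before the injection and again at Visit 4.

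The Covariates paragraph names age, sex, race and BMI, because biomarker levels differ by them, and says that "these patient factors will be collected and used as covariates in our statistical analyses". Meniscal procedure is not on the list. The Statistical Analysis Plan, two sentences at the end of the document, names no covariate: "Primary objective will be assessed using two-tailed independent t-tests for comparison between timepoints". Secondary measures are treated the same way.

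Background gives the protocol's own reason to care about this tissue: "the meniscus plays an active role in promoting the cycle of articular cartilage degradation and PTOA progression after ACL reconstruction".

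**The concern.** One operation removes part of the meniscus and the other keeps it. If bone shape, uCTX-II or knee scores change at different rates after the two, the procedure is a prognostic factor. Using within-patient change removes differences in starting size but not differences in rate of change.

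With about 15 patients per arm, chance can leave the arms with noticeably different shares of each operation. Nothing in the plan limits this at allocation or accounts for it in the analysis, although the procedure is known at surgery, weeks before the injection. At stake are the precision of the treatment comparison and how far one observed difference can be read as the effect of the injection.

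**Working it through.** **Inputs from the documents.** N = 30; two eligible operations; independent t-tests, two-tailed, no covariates. The only basis given for N is recruitment yield, 100 × 0.30 = 30, which reproduces. No alpha, power, SD or effect size is stated.

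**Assumptions.** 15 per arm; alpha 0.05; one procedure in 30 to 50% of patients; a procedure effect g of 0.5 or 1.0 within-procedure SD; the SAP's t-tests compare the arms on change.

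**1. How often are the arms unbalanced?** Take the number of patients with one procedure in each arm as independent Binomial(15, p).

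| Difference between arms | p = 0.5 | p = 0.3 |
|---|---|---|
| at least 3 (3/15 = 20 points) | 0.362 | 0.318 |
| at least 4 (4/15 = 27 points) | 0.200 | 0.161 |
| at least 5 (5/15 = 33 points) | 0.099 | 0.071 |

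If instead exactly K of the 30 had one procedure and the split is exactly 15:15 (hypergeometric), the chance of a difference of at least 4 is 0.11 for K = 9, 0.26 for K = 12 and 0.14 for K = 15. The order of magnitude is the same.

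**2. How far does an imbalance move the comparison?** Shift = g × (difference in patients)/15. For 4 patients: 0.5 × 4/15 = 0.13 SD; 1.0 × 4/15 = 0.27 SD. For scale, the standard error of the arm difference within procedure is √(2/15) = 0.365 SD, and 15 per arm detects 1.06 SD with 80% power.

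**3. Error rate in one unbalanced trial.** For a 5-patient imbalance the shift is g/3. The noncentrality is (g/3)/[√(1 + 0.24g²) × √(2/15)], where 0.24 = 0.4 × 0.6 stands for the mix.
- g = 0.5: 0.167/(1.030 × 0.365) = 0.44, so two-sided type I error is about 0.07.
- g = 1.0: 0.333/(1.114 × 0.365) = 0.82, so about 0.12.

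**4. Error rate averaged over randomisations.** Simulating the unstratified t-test (12,000 trials per setting, 15:15, even mix, no treatment effect) gives 0.051 at g = 0.5 and 0.054 at g = 1.0. The test remains valid.

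**5. Loss of precision.** At an even mix, the SE of the unadjusted difference is about √[(2/15)(1 + g²/4)]: 0.376 at g = 0.5 and 0.408 at g = 1.0, against 0.365 if procedure is removed. Simulated power at a true effect of 1.06 SD:

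| Allocation and analysis | g = 0.5 | g = 1.0 |
|---|---|---|
| unstratified, t-test | 0.774 | 0.706 |
| unstratified, procedure in model | 0.783 | 0.788 |
| stratified, t-test | 0.781 | 0.714 |
| stratified, procedure in model | 0.795 | 0.802 |

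**6. Why stratifying alone does not help.** Stratification brings the true SE down to about 0.365, but at g = 1.0 the t-test still estimates about 0.408. The effective critical value rises from 2.048 to 2.048 × 0.408/0.365 = 2.29 on 28 degrees of freedom, a true level of about 0.03. The simulation also gives 0.03.

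**The case against.** The case against has four parts.

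First, a reader might infer that the trial uses simple, unstratified randomisation. The documents do not say so; they are silent on method. What they support is that no stratification is stated, and the imbalance figures apply only if allocation ignores procedure. This stands.

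Second, a reader might infer that the result would be confounded by the operation. It would not be, in the sense of bias. Chance imbalance is already part of the t-test's error rate, and it is as likely to hide an effect as to mimic one. This also stands.

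Third, a reader might take Background as saying that repair and meniscectomy lead to different outcomes. It does not compare them; it describes the role of meniscal tissue in general, and every participant has a meniscal injury. The documents also do not say whether tears are medial or lateral, which could matter as much for a medial condyle measure. So the procedure effect is plausible but assumed.

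Fourth, the gain is small at g = 0.5 (power 0.774 to 0.795). True, and the 4-patient shift of 0.13 SD is well below the standard error of 0.365 SD. The larger gain needs g = 1.0, for which the documents give no evidence.

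The omission itself remains. The protocol plans to adjust for traits linked to biomarker levels but not for the one surgical difference written into its eligibility criteria, and the SAP carries out no adjustment at all.

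**Conclusion.** The point holds as a low-cost improvement to precision and interpretability, not as a threat to validity. Meniscal procedure is absent from the stated allocation, from the covariate list and from the SAP. A difference of 4 or more patients between arms is expected in about 16 to 20% of trials under simple allocation, assuming 15 per arm and 30 to 50% prevalence. Type I error stays about 5% on average.

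If the procedures differ by 0.5 SD or less, the loss is modest. At 1.0 SD, stratifying and adjusting would raise power from about 0.71 to 0.80, and a single trial with a 5-patient imbalance would run at about 0.12 instead of 0.05. Neither the procedure effect nor the mix is in the documents, so these figures are a range and not an estimate for this trial.

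**What to change.** - **Analysis (the essential part).** Replace the t-test for each change endpoint with a linear model containing treatment and meniscal procedure, coded as partial meniscectomy alone versus any repair, and prespecify it in the SAP.
- **Allocation.** State the randomisation method. If randomisation has not begun, use blocked 1:1 allocation stratified by this one factor. If stratifying is not feasible, prespecify the adjustment alone; it recovers most of the gain (power 0.783 to 0.788). Do not stratify and keep the plain t-test, which becomes conservative.
- **Consistency.** Reconcile the Covariates paragraph with the SAP by stating which of age, sex, race and BMI enter which model, if any.

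The cost is one degree of freedom (28 to 27), possibly one unfinished block per stratum, a second short allocation list, and rewriting the two-sentence SAP. Procedure is known at surgery and the injection follows at eight weeks, so nothing is delayed.
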